5.3.3. Patient-Reported Outcome Analysis Variables

Definitions of variables for PRO analyses are listed below alphabetically.

- Average Symptom Burden Index (ASBI) is calculated as the mean of the 6 symptom items of the LCSS. The ASBI will not be computed for a patient if he/she has one or more missing values for the 6 items. Refer to Section 10.2.1 of the protocol for the definition of the LCSS.
- EQ-5D-5L index score is calculated as recommended by EuroQol (EQ-5D-5L User Guide, www.euroqol.org). Index score and visual analog scale (VAS) will be calculated for each assessment period as per current recommendations (van Hout et al. 2012). The index score is calculated from a set of item weights to derive a score of -0.285 to 1, with 1 representing the best health status. United Kingdom (UK) weights will be applied for the base case. The index score will not be computed for a patient if he/she has one or more missing values for the 5 items.
- Change from baseline for each LCSS or EQ-5D item at any postbaseline visit is calculated by subtracting baseline assessment result from the current assessment result.
- LCSS total score is calculated as the mean of the 9 LCSS items. The LCSS total score will not be computed for a patient if he/she has one or more missing values for the 9 LCSS items.
- **Maximum change** for each LCSS item is defined as the largest decrease from baseline, which is the smallest (that is, most negative or smallest positive) non-missing value among all change from baseline values.
 - **Note.** Negative values of change from baseline (that is, decreases in the LCSS score towards the lower end of the symptom scale) indicate improvement in symptoms. For a patient and given LCSS item, if all change values are positive, the smallest positive change will be the maximum change; if at least one change value is negative, the most negative value will be the maximum change.
- Time to deterioration (TtD) for each of the 9 LCSS items, ASBI, and the LCSS total score is defined as the time from the date of randomization until the date of the first ≥15-mm increase from baseline (de Marinis et al. 2008). Alternative definitions of minimally important differences may be explored as needed. Patients without deterioration will be censored on the date of the patient's last postbaseline LCSS assessment for this item or randomization date, whichever is last.

5.3.4. Exploratory Analyses Variables

• Time to deterioration (TtD) in Eastern Cooperative Oncology Group (ECOG) performance status (PS) is defined as the time from the date of randomization to the first date observing a change (that is, deterioration) in ECOG PS to ≥2. Variations of the definition are: 1) a change to ≥3, 2) a change of ≥2 levels from baseline, and 3) a change of ≥1 level from baseline. Censor at time of the last ECOG PS value if no event.

- **Progression-Free Survival 2 (PFS2) (Part B)** is defined as the time from randomization to second disease progression (defined as objective radiological or symptomatic progression after start of additional systemic anticancer treatment), or death from any cause, whichever occurs first.
- Time to diagnosis of CNS (brain or meninges or spinal cord) metastases is defined as the time from randomization to CNS metastases. Patients without CNS metastases at the time of data inclusion cut off will be censored at the date of last postbaseline adequate radiological tumor assessment or at randomization if no post-baseline assessment.
- Time to response is defined as time from randomization to response (CR or PR) for those patients that responded only.

The exploratory analyses variables defined below are only applicable for Part C.

- 1-year PFS rate is defined as the cumulative proportion of patients who survived during the first year (that is, 1 year from enrollment) in the study without disease progression. Patients who have neither progressed nor died will be censored at the day of their last radiographic tumor assessment.
- Progression-free survival in Part C, Period 2 is defined as the duration from the date of last tumor measurement before osimertinib treatment to occurrence of PD or death from any cause, whichever occurs first.
- **PFS2 (Part C)** is defined as the duration from enrollment (assignment to treatment) to the second occurrence of PD or death from any cause, whichever occurs first.
- Overall survival (OS) in Part C, Period 2 is defined as the duration from the date of last tumor measurement before osimertinib treatment to the date of death. For each patient who is not known to have died as of the data cut-off date for a particular analysis, OS will be censored for that analysis at the date of last contact prior to the data-inclusion cut-off date (contacts considered in the determination of last contact date include AE date, lesion assessment date, visit date, and last known alive date).

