5.1.2. Part B

The study will enroll approximately 450 patients in 1:1 randomization (that is, approximately 225 patients will be randomly assigned to each treatment arm). The primary PFS analysis will be performed after approximately 270 PFS (approximately 40% censoring rate) events.

An interim futility analysis was conducted at 114 investigator-assessed PFS events (data cutoff date 16 October 2017), and the IDMC recommended the trial continue without modification. A nominal 1-sided alpha <0.00001 was spent in order to maintain type-I error. Assuming an HR of 0.71, this sample size yields at least 80% statistical power to detect superiority of the ramucirumab plus erlotinib arm over the placebo plus erlotinib arm, with the use of a 1-sided log-rank test and a type I error of 0.02499. If the true median PFS for the placebo plus erlotinib arm is 11 months, then the HR of 0.71 amounts to an approximate 4.5-month improvement in median PFS for the ramucirumab plus erlotinib arm under an additional assumption of exponential survival distribution.

Sample size calculation is carried out in EAST Version 6.4 (1994-2016).

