Statistical analysis of this study will be the responsibility of Lilly or its designee. The study PK scientist will be responsible for designing, conducting, and interpreting the PK analysis and delivering PK parameters. The interpretation of final study results will be the responsibility of the clinical research physician (CRP) and the study statistician. These individuals will also be responsible for the appropriate conduct of an internal review process for both the CSR and any study-related material to be authorized for publication by Lilly.

The following general terms will be used globally in the SAP:

- Unless otherwise specified, **summary statistics** stand for n, mean, standard deviation, median, Q3-Q1, minimum, and maximum for continuous variables; and frequency and percentage for categorical variables.
- Study period

- O Dose-limiting toxicity (DLT) assessment period for Part A: for individual patient assessment, period begins on the day of the first study drug dose and ends on the day when the patient:
 - o completed 2 cycles of treatment, or
 - o discontinued from study treatment or study participation before completing 2 cycles due to a DLT.

Note. Two cycles are considered completed on the 14th day from the second dose of ramucirumab.

- o **Study treatment period** begins at the first dose of study treatment and ends when the patient and the investigator agree that the patient will no longer continue any study treatment. The date of this agreement is to be reported on the electronic case report form (eCRF) as the Date of Discontinuation from all study treatment.
- o **30-day short-term follow-up period** begins the day after the patient and the investigator agree that the patient will no longer continue any study treatment and lasts approximately 30 days (± 3 days).
- O Long-term follow-up period begins the day after short-term follow-up is completed and continues every 6 weeks (± 7 days) until progressive disease (PD), thereafter every 3 months (± 7 days) until the patient's death, withdrawal of consent to participate or overall study completion, whichever occurs first.

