5.3.1. Efficacy Analysis Variables

Definition of efficacy analysis variables are listed below in order of importance.

Progression-free survival (PFS) is defined as the time from the date of randomization until the date of radiographic documentation of progression (as defined by RECIST v. 1.1) or the date of death due to any cause, whichever is earlier. Table JVCY.5.1 lists rules for determining date of progression or censor for PFS. The censoring is taken in the following order:

- If a patient does not have a baseline disease assessment, then the PFS time will be censored at the randomization date, regardless of whether or not objective PD or death has been observed for the patient; otherwise,
- If a patient is not known to have died or have PD as of the data-inclusion cut-off date for the analysis, the PFS time will be censored at the date of last postbaseline adequate radiological tumor assessment, or at the date of randomization if the patient does not have any postbaseline adequate radiological assessment.

Note. If there are multiple dates associated with one radiological tumor assessment, the assessment date will be set to the first date when the overall response is PD and the last date otherwise. A radiological tumor assessment is considered adequate if its response is among CR, PR, SD, or PD.

PFS (day) = Date of progression or death / censor - Date of randomization + 1.

Table JVCY.5.1. Rules for Determining Date of Progression or Censor for Progression-Free Survival

Rule	Situation	Date of Progression or Censor	Outcome
1	No baseline tumor assessments	Date of Randomization	Censored
2	No postbaseline assessments and no death	Date of Randomization	Censored
3	No documented progression and no death (with a postbaseline tumor assessment)	Date of last adequate tumor assessment	Censored
4	Patient lost to follow-up (or withdrew consent from study participation) before documented progression or death	Date of last adequate tumor assessment	Censored
5	Documented progression	Date of documented progression	Progressed
		If a tumor assessment was done on multiple days, use the earliest date for that visit.	
6	Death without documented progression	Date of death Progresse	
7	Documented progression or death after missing ≥2 consecutive postbaseline tumor assessments	Date of last adequate tumor assessment before missed assessments or date of randomization, whichever is later	

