5.11.3. Exploratory Efficacy Analyses

Time to deterioration in ECOG PS and its variations will be analyzed using the Kaplan-Meier method and compared using an unstratified log-rank test. The association between PFS event and ECOG PS deterioration will be assessed through an analysis of change from baseline in ECOG PS by objective progression (yes versus no) by tumor measurement period.

Time to diagnosis of CNS metastases will be analyzed using the Kaplan-Meier method and compared using an unstratified log-rank test for Part B only. For Part C, time to diagnosis of CNS metastases will be analyzed using the Kaplan-Meier method.

A waterfall plot of the (best) percent change from baseline in target lesion measurement will be generated for each study arm in Part B and Part C period 1.

Regarding PFS2 in Part B and PFS in Part C Period 2, the median with 95% CI, and progression free survival rates at various time points will be estimated using Kaplan-Meier method (Kaplan and Meier 1958).

A 1-year PFS rate of Part C, i.e., a cumulative proportion of patients who survived during the first year (that is, 1 year from enrollment) in the study without disease progression, will be estimated using Kaplan-Meier method (Kaplan and Meier 1958) in addition to PFS curves, the median with 95% CI, and survival rates at various time points, for Part B and C, respectively.

For PFS2 and OS in Part C Period 2, the median with 95% CI will be estimated using Kaplan-Meier method (Kaplan and Meier 1958) for patients that receive osimertinib after disease progression.

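### Time to CNS metastases counts diagnoses up to the data cut-off but censors other patients at their last adequate scan; if later diagnoses are recorded and scans largely stop at progression, CNS rates are inflated and the arm comparison can lean towards ramucirumab.

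*SAP*

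**What the plan says.** Section 5.3.4 says that the endpoint "is defined as the time from randomization to CNS metastases". It does not tie the event to a scheduled scan, to the time before first progression, or to the time before new therapy. The censoring rule reads: "Patients without CNS metastases at the time of data inclusion cut off will be censored at the date of last postbaseline adequate radiological tumor assessment", with randomization as the fallback date. Under Section 5.3.1, "A radiological tumor assessment is considered adequate if its response is among CR, PR, SD, or PD".

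Section 5.2 describes long-term follow-up that "continues every 6 weeks (± 7 days) until progressive disease (PD), thereafter every 3 months (± 7 days) until the patient's death". It does not say which of those visits include a scan.

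Section 5.11.3 fixes the method: "Time to diagnosis of CNS metastases will be analyzed using the Kaplan-Meier method and compared using an unstratified log-rank test for Part B only". Part C gets a Kaplan-Meier estimate only. Section 5.11.5 lists no sensitivity analysis of the CNS rule.

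**The concern.** Event status is judged at the data cut-off, but a patient without an event is moved back to the last adequate scan. Take two patients with non-CNS progression whose last adequate scan is the one showing it. One is diagnosed with CNS metastases eight months later and contributes those eight months plus an event. The other stays alive and free of CNS disease for the same eight months and contributes neither. After the last scan, the risk set then holds mainly people who will become cases. Kaplan-Meier and log-rank methods assume that staying at risk does not depend on the future outcome, and here it can. Treating death as a competing event would not repair this.

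Two consequences could follow. CNS rates would be overstated in both arms. The overstatement would be larger in the arm that progresses earlier, so a PFS benefit could show up as an apparent CNS benefit.

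The SAP's other time-to-event rules match their windows better. PFS rules 7 and 8 in Table JVCY.5.1 cut off events that follow missed assessments or new therapy. OS follows event-free patients to the last date known alive. ECOG deterioration takes events and censoring from the same assessments.

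**Working it through.** The SAP gives no figure for the CNS endpoint, so the size was found by simulation on the Part B PFS design.

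**Step 1: reproduce the PFS inputs (Section 5.1.2).**
- Power with 270 events, HR 0.71, one-sided alpha 0.02499 (Schoenfeld): Φ(√270/2 × |ln 0.71| − 1.960) = Φ(2.814 − 1.960) = Φ(0.854) = 80.3%. The SAP says at least 80%.
- Ramucirumab median: 11/0.71 = 15.5 months, a gain of 4.5 months, as stated.

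**Step 2: main setting, no true CNS effect.**
- From the SAP: "The study will enroll approximately 450 patients in 1:1 randomization", so 225 per arm; PFS medians 11 and 15.5 months; cut-off at 270 PFS events.
- Assumed, not in the SAP: CNS hazard 0.006 per month in both arms, before and after progression; 24-month accrual; median survival after progression 20 months; 6-weekly scans that end at progression.
- True 24-month net CNS rate: 1 − exp(−0.006 × 24) = 13.4% in both arms.

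| Share of post-progression CNS diagnoses recorded | 24-month rate, placebo vs ramucirumab | HR | Two-sided rejection |
|---|---|---|---|
| All | 21.7% vs 18.3% | 0.88 | 8.6% |
| Half | 17.4% vs 15.6% | 0.93 | 6.1% |
| A quarter | 15.1% vs 14.1% | 0.97 | 5.2% |
| Matched window | 12.7% vs 12.9% | about 1.0 | about 4–6% |

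With all later diagnoses recorded, the overstatement is 21.7 − 13.4 = 8.3 points on placebo and 18.3 − 13.4 = 4.9 points on ramucirumab.

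**Step 3: a second set of assumptions.** CNS hazard 0.01 per month, median survival after progression 15 months, 28-month accrual, cut-off at 40 months. Again no true CNS effect.
- SAP rule, all recorded: HR 0.86, rejection 11.5%, 24-month rates 31.7% vs 27.7%.
- Matched window: HR 0.99, rejection 4.9%, 22.0% vs 21.8%.
- Everyone followed to death or cut-off: HR 1.00, rejection 4.8%, 21.3% vs 21.3%.
- Half recorded: HR 0.92, rejection 6.7%.
- Hazard varied, all recorded: at 0.005 per month, HR 0.85 and rejection 8.4%; at 0.02 per month, HR 0.87 and rejection 14.3%.

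**Step 4: where the bias disappears (second set of assumptions).**
- No later diagnosis recorded: HR 0.99.
- Half of patients keep 3-monthly scans after progression: HR 0.94.
- All keep them: HR 0.99, with rates about 1 point too high.
- Equal PFS in the two arms: HR 1.00, although rates are still inflated (31.7% against 21.2%).

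**The case against.** The strongest reply is that the bias depends on facts the SAP does not state. CNS diagnoses after the last adequate scan must be collected and dated, and scans must largely stop at progression. Section 5.2 gives visit intervals and does not mention scans. The PFS2 definition includes "objective radiological or symptomatic progression after start of additional systemic anticancer treatment", so some radiology after first progression is expected. A matched reading is also possible. Section 5.8 derives baseline metastatic sites from radiographic data; if CNS events also came only from tumor assessment records, a new CNS lesion would be a PD assessment, hence adequate, and the two windows would coincide. All of this stands and makes the point conditional. It does not remove it, because the SAP names no event source and sets no limit on the event. The same PFS2 wording shows that disease events after first progression are collected.

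A reader might infer three stronger things that the document does not support.
- That bias is established. It is not, for the reasons above.
- That false-positive rates reach the levels simulated with a CNS hazard that doubles after progression. That setting is not a null: delaying progression then truly delays CNS metastases, and complete follow-up itself gives HR about 0.92 to 0.94. Those figures should not be read as error rates.
- That Part C is affected in the same way and needs a cut at first progression. Patients entering Period 2 are assessed for progression again (Sections 5.3.4 and 5.11.3), so their last adequate scan is not at first progression.

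Finally, the endpoint is exploratory and outside the PFS–OS testing hierarchy, which limits the weight of the point.

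**Conclusion.** The mismatch between the event and censoring windows is in the text, and nothing else in the SAP closes it. Whether it biases the result depends on data collection that the SAP does not describe. If later CNS diagnoses are recorded, scans largely stop at progression and PFS differs as planned, the comparison leans towards ramucirumab. At the assumed hazard of 0.006 per month, HR is about 0.88 at full capture and close to 1 at low capture; two-sided rejection is roughly 6–9% between half and full capture. Higher assumed hazards give higher rejection. Inflation of the rates needs only the first two conditions; the lean between arms also needs the PFS difference. The CNS hazard, accrual and survival after progression are assumptions, so the direction is firmer than the size. This is a minor point on an exploratory endpoint, worth correcting because the correction is cheap.

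**What to change.** In Section 5.3.4, use one window for events and censoring. Count a CNS metastasis as an event only if it is diagnosed on or before the patient's last adequate radiological tumor assessment, and censor everyone else, including patients diagnosed later, at that assessment. Name the data source for the event. State also that, after first progression, a scan prompted by suspected CNS disease does not by itself extend the window; otherwise the asymmetry returns.

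As a supportive analysis, count all CNS diagnoses to the data cut-off, with patients without one followed to the last contact at which CNS status was ascertained.

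In Part C, apply the same matched-window principle with Period 2 assessments included, not a cut at first progression.

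The cost is a few sentences of SAP text and one programming condition, plus the supportive run. The small downside is that some late CNS diagnoses appear only in the supportive analysis.

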5.4. Handling of Dropouts or Missing Data

Rules for handling dropouts or missing data are listed by type of analysis alphabetically. Unless otherwise specified, observed data will be used and missing data will not be imputed or carried forward.

General rules for imputing dates related to AE or concomitant therapy:

- Onset date of an AE or start date of a concomitant therapy:
 - o If only the day is missing, the date will be set to:
 - First day of the month that the event occurred, if the onset yyyy-mm is after the yyyy-mm of first study treatment.

- The day of the first study treatment, if the onset yyyy-mm is the same as yyyy-mm of the first study treatment.
- o If both the day and month are missing, the complete date will be set to:
 - January 1 of the year of onset, if the onset year is after the year of the first study treatment.
 - The date of the first dose, if the onset year is the same as the year of the first study treatment.
- Resolution date of an AE or end date of a concomitant therapy:
 - o If only the day is missing, the date will be set to the last day of the month of the occurrence, or to the date of death if the patient died in the same month.
 - o If both the day and month are missing, the date will be set to 31 December of the year of occurrence.

If a date is completely missing, then the AE will be considered treatment emergent. In case of additional therapies, the therapy will be considered concomitant.

General rule for imputing other dates: If a date variable is needed for an analysis, use the following general rule to impute incomplete date:

- If the date has no missing year and month but the day is missing, then assign Day 1 to the day
- If the date has no missing year, but has missing month, then assign January to the month.

However, after imputation, check if the imputed date is logically consistent with other relevant date variable(s) and make appropriate correction if necessary. For example, if a visit start date was 10 May 2015 and a tumor assessment date was xx May 2015 (missing day) but it was known that it occurred after that visit, then after imputation, the tumor assessment date became 01 May 2015. In this case, the imputed tumor assessment date should be compared to the visit start date and then corrected to be the visit start date, 10 May 2015.

Patient-reported outcome analysis: For percentage compliance of the LCSS and EQ-5D-5L, instruments with at least one item completed will be considered as having been completed. No other adjustment or imputation for missing data will be performed.

Safety analysis: The following rule for missing data processing will apply for safety analysis:

- Missing classifications concerning study medication relationship will be considered as related to study medication.
- If the AE onset date is missing or partial, the date will be compared as far as possible with the date of first dose of study medication when determining whether or not the AE is present at baseline. In this case, the AE will be assumed to be treatment emergent, unless there is clear evidence (through comparison of partial dates) to suggest that the AE started prior to the first dose of study medication.

Time-to-event analysis: All censored data will be accounted for using appropriate statistical methods. See Sections 5.3.1 and 5.11 for details.

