5.9. Concomitant Medications

A medication will be regarded as concomitant if:

• the medication was started on or after the date of first dose of study treatment and before the end of short-term follow-up;

• the medication was started prior to first dose of study treatment but was ongoing at the time of the first dose of study treatment.

The following concomitant medications used in study treatment period or the 30-day short-term postdiscontinuation follow-up period will be summarized by numbers and percentages by treatment arm, presented in decreasing frequency of the World Health Organization (WHO) drug term across treatment arms:

- All concomitant medications
- Best supportive care and select concomitant medications, including antidiarrheal agents, antiemetic agents, analgesic agents, antibiotics, antihypertensives, antifungals, antivirals, appetite stimulants, granulocyte-colony stimulating factor, erythroid growth factors, rash treatment and bisphosphonates.
 - **Note.** Such drugs to be used for programming will be identified through reviewing of the unique drug terms collected in the study.
- Premedication for ramucirumab/placebo.

The proportions of patients receiving at least one concomitant medication and the proportion reporting use of concomitant medications will be compared between the treatment arms using the Chi-square test for Part B. The concomitant medications will be summarized for Parts A and C. Patient listing of all concomitant therapies and premedications will be provided.

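### Section 5.4 sets a partial start date in the month or year of first dose to first dose without looking at a recorded end date, so a medication stopped before treatment can be classed as concomitant

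*SAP*

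**What the plan says.** SAP Section 5.4 has a block headed "General rules for imputing dates related to AE or concomitant therapy". For an onset or start date with the day missing, it assigns "The day of the first study treatment, if the onset yyyy-mm is the same as yyyy-mm of the first study treatment". With day and month both missing, it assigns "The date of the first dose, if the onset year is the same as the year of the first study treatment". Neither bullet mentions the end or resolution date. Partial end dates are imputed late: "If only the day is missing, the date will be set to the last day of the month of the occurrence". A death in that month is an exception, and 31 December is used if the month is also missing. Complete end dates stay as recorded.

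A second block follows, opening with "General rule for imputing other dates: If a date variable is needed for an analysis". After its two bullets comes an instruction to "check if the imputed date is logically consistent with other relevant date variable(s) and make appropriate correction if necessary", illustrated by a tumor assessment date.

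Further on, the safety part of Section 5.4 assumes that an AE with a missing or partial onset is treatment-emergent, with this exception: "unless there is clear evidence (through comparison of partial dates) to suggest that the AE started prior to the first dose of study medication".

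Section 5.9 counts a medication as concomitant in two cases. The first is that "the medication was started on or after the date of first dose of study treatment and before the end of short-term follow-up". The second is that it began before first dose and was still ongoing then. The tabulations are of concomitant medications used during treatment or the 30-day follow-up. For Part B, the proportion of patients with at least one concomitant medication is compared between arms by a chi-square test.

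**The concern.** A rule that fills in a start date should not contradict another date on the same record. Here the two start-date bullets look only at whether the known month or year matches that of first dose. If the record also carries an end date before first dose, the imputed start comes after the end.

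For medications this matters because the first criterion in Section 5.9 depends on the start date alone. The second criterion, ongoing at first dose, shows that a drug stopped before treatment is not meant to count. The imputation moves such a drug out of reach of the second criterion and into the first. Medications known to have stopped before treatment could then enter on-treatment summaries and a formal comparison between arms.

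For AEs, the imputed onset falls on Day 1 while the safety rule in the same section would class the event as not treatment-emergent. The date and the classification then disagree.

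**Working it through.** The SAP gives no figure on this point, so the check traces the date rules on two constructed records. All dates are assumed.

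**Record 1, day missing.** First dose 20 May 2016; start known only as May 2016; recorded end 10 May 2016.
- The start month equals the month of first dose, so Section 5.4 sets the start to 20 May 2016.
- The end date is complete and stays at 10 May 2016.
- The duration formula in Section 5.3 is end minus start plus 1: 10 − 20 + 1 = −9 days. The imputed start is 10 days after the end.

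**Record 2, day and month missing.** First dose 20 August 2016; start known only as 2016; recorded end 12 March 2016.
- The start year equals the year of first dose, so the start becomes 20 August 2016.
- From 12 March to 20 August is 19 + 30 + 31 + 30 + 31 + 20 = 161 days, so the duration is −161 + 1 = −160 days.

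The negative durations only show that the dates are inconsistent; the medication and AE sections plan no analysis of these durations.

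**When the conflict can arise.** With a month-level start, it needs a complete end date earlier in the same month as first dose, because an end date without a day is moved to month end. With a year-level start, it needs an end date in the same year, either complete and before first dose or known to an earlier month. An end date known only to the year becomes 31 December and causes no conflict.

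**If the record is a medication.**
1. First criterion in Section 5.9, started on or after first dose: met, because the imputed start is the first-dose date.
2. Second criterion, started earlier and ongoing at first dose: not met.
3. One criterion is enough, so the medication is concomitant by definition although it had stopped.
4. The safety rule quoted above speaks only of AEs and does not help.

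**If the record is an AE.**
1. The imputed onset is the first-dose date.
2. Under the safety rule, the event is treatment-emergent unless there is clear evidence of an earlier start. Resolution before first dose is such evidence, so the event should not be treatment-emergent.
3. The rule refers to comparing partial dates and does not name the resolution date. The onset's matching month or year, compared with first dose, gives no evidence by itself. The classification is therefore right on a sensible reading, but the imputed onset contradicts it.

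**The case against.** The other side has four arguments.

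- **The summary window in Section 5.9.** The tabulations cover medications used during treatment or the 30-day follow-up, and a drug stopped earlier was not used then. This has force, and a careful programmer might apply it. But it limits a set already labelled concomitant and gives no end-date test. The chi-square comparison of patients with at least one concomitant medication rests on the definition, whose first criterion uses the start date alone.
- **The consistency check.** A start after its own end is a plain inconsistency, and the check would correct it if it applied. It is a separate paragraph, and nothing expressly excludes AE or therapy dates. Yet it follows the rule for other dates and its example is a tumor assessment, so its scope is at best unclear.
- **AEs are already handled.** This stands. A reader might infer that AEs resolved before first dose will be counted as treatment-emergent. The document does not support that, because the exception for clear evidence of a pre-dose start covers them.
- **The default is conservative.** Assigning first dose when timing is unknown is reasonable and agrees with how the SAP treats completely missing dates. That justification does not reach a record whose own end date shows that it was over before treatment. Section 5.4 says that observed data will be used unless otherwise specified.

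A reader might also infer that nothing in the SAP could keep stopped medications out, or that the comparison between arms is distorted by a known amount. Neither follows: the first two arguments offer possible routes, and the document has no data on how often such records occur.

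**Conclusion.** The point holds in a limited form. The start-date rules for AEs and therapies lack an end-date condition and can place a start after a known end. Read literally, a medication stopped before first dose then meets the concomitant definition and can enter the chi-square comparison. The wording that might prevent this is not clearly applicable. For AEs, the SAP already points to the right classification, and only the imputed onset date is at odds with it.

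This is a minor matter. It affects medication summaries and possibly a few AEs. The number of records cannot be derived from the document: it depends on how often start dates are partial and on whether medications stopped before treatment are recorded in the same data. PFS and OS do not use these rules and are unaffected.

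**What to change.** In the AE and concomitant-therapy block of Section 5.4:

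1. Set a partial onset or start to first dose only when the end or resolution date is missing, ongoing, or on or after first dose.
2. Otherwise impute the start no later than the recorded end. Class the medication as prior and the AE as not treatment-emergent, in line with the safety rule in the same section.
3. State that the consistency check also covers AE and concomitant-therapy dates.

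The cost is one condition in the SAP and in the derivation program, with no new data. Section 5.2 allows clarifications of this kind in the SAP before the aggregate database is unblinded.
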